5.4.2 Analysis supporting secondary objective(s)

5.4.2.1 Logistic regression

Binary outcome variables including UAS7=0 “Complete Response” or UAS7 \leq 6 “Disease control” will be evaluated using a logistic regression model with treatment, and actual randomization strata variables (i.e. geographic region and prior exposure to anti-IgE biologics). Odds ratios will be computed for treated participants with response relative to control participants utilizing the logistic regression model fitted.

The odds ratio will be calculated such that an odds ratio > 1 is favorable for LOU064 drug. The SAS procedure PROC LOGISTIC will be used for this analysis with the following code:

```
proc logistic data = ...;
by_imputation_;
class trt01p antige region/ param = glm;
model response (event = '1') = trt01p antige region baseline;
estimate "LOU064 vs Placebo" trt01p 1 -1;
```

```
ods output ESTIMATEs=estimates;  
run;
```

If separation occurs, the Firth's method will be implemented using the firth option in the MODEL statement.

The SAS procedure PROC MIANALYZE will be used to combine the results. The odds ratios and the 95% confidence interval for the odds ratio will be generated using an exponential transformation of the model estimates.

5.4.2.2 Covariate adjustment for treatment difference with binary outcome variable

For binary outcome variables, the treatment difference and the corresponding 95 % confidence interval will be provided besides odds ratios.

FDA guidance introduces the following steps for one statistically reliable method of covariate adjustment for treatment difference with binary outcome ([Adjusting for Covariates in Randomized Clinical Trials for Drugs and Biological Products, Guidance for Industry, Draft guidance, May 2021](#)).

5.4.2.3 Negative binomial regression

Count variable including the cumulative number of weeks achieving AAS7= 0 response between baseline and Week 12 or the cumulative number of weeks achieving UAS7≤6 response will be modelled using a negative binomial regression model with log link, using treatment group, randomization strata factors (i.e. geographic region and prior exposure to anti-IgE biologics, and baseline AAS7=0 status (for AAS7 = 0 response only). The patient's time in the treatment period up to Week 12 (natural log of proportion of time in treatment period, i.e., natural log of [number of weeks with the response variable in treatment period/12 weeks]) is used as an offset variable. The patient's time in the treatment period up to Week 24 (natural log of proportion of time in treatment period, i.e., natural log of [number of weeks with the response variable in treatment period/24 weeks]) is used as an offset variable.

If the AAS7 = 0 (respectively UAS7≤6) assessment is missing, it will be considered as a non-response for the cumulative number of weeks that participants achieve AAS7= 0 response calculation (respectively UAS7≤6).

The negative binomial model accounts for any over dispersion that may result from assuming a Poisson distribution by allowing a different Poisson rate for each patient and assuming that these rates as a set are distributed across participants according to a gamma distribution.

The SAS procedure PROC GENMOD will be used for this analysis with the following code:

```
proc genmod data=...;  
  by impnb;  
  class trt01p antige region/ param = glm;  
  model count = baseline trt01p antige region/ DIST= NEGBIN LINK= LOG  
  offset=offset;  
  lsmeans trt01p / cl exp diff ilink e OM;  
  estimate "LOU064 v.s pbo" trt01p 1 -1;
```

```
ods output Estimates=estimates LSMeans=lsmeans;
run;
```

where baseline = baseline AAS7=0 status (for AAS7 = 0 response only).

The SAS procedure PROC MIANALYZE will be used to combine the results. The risk ratio and the 95% confidence interval for the risk ratio will be generated using an exponential transformation of the model estimates.

5.4.2.4 Exposure adjusted incidence rate and 100*(1- α)% confidence interval

It will be assumed that for each of n participants in a clinical trial the time t_j ($j=1, \dots, n$) to the first occurrence of a certain event is observed, or if the event was not experienced, the (censored) time to the end of the observation period. The sequence of first occurrences of an event will be modeled to follow approximately a Poisson process with constant intensity θ . The rate

parameter θ will be estimated as $\lambda=D/T$, where $T=\sum_{j=1}^n t_j$ and D is the number of participants

with at least one event. Conditionally on T, an exact 100*(1- α)% confidence interval for a Poisson variable with parameter θT and observed value D can be obtained based on ([Garwood, 1936](#)), from which an exact 100*(1- α)% confidence interval for D/T will be derived as follows ([Sahai, 1993](#); [Ulm, 1990](#)):

$$\text{Lower confidence limit } L = \frac{0.5c_{\alpha/2,2D}}{T} \text{ for } D>0, 0 \text{ otherwise,}$$

$$\text{Upper confidence limit } U = \frac{0.5c_{1-\alpha/2,2D+2}}{T}$$

where $c_{\alpha,k}$ is the α^{th} quantile of the Chi-square distribution with k degrees of freedom.

5.4.2.5 Exposure adjusted occurrence rate and 100*(1- α)% confidence interval

It will be assumed that for each of n participants in a clinical trial the time t_j ($j=1, \dots, n$) is the observation period. The number of occurrences of the event will be modeled to follow approximately a Poisson process with constant intensity θ . The rate parameter θ will be

estimated as $\lambda=D/T$, where $T=\sum_{j=1}^n t_j$ and D is total number of events. Conditionally on T, an

exact 100*(1- α)% confidence interval for a Poisson variable with parameter θT and observed value D can be obtained based on ([Garwood, 1936](#)), from which an exact 100*(1- α)% confidence interval for D/T will be derived as follows ([Sahai, 1993](#); [Ulm, 1990](#)):

$$\text{Lower confidence limit } L = \frac{0.5c_{\alpha/2,2D}}{T} \text{ for } D>0, 0 \text{ otherwise,}$$

$$\text{Upper confidence limit } U = \frac{0.5c_{1-\alpha/2, 2D+2}}{T}$$

where $C_{\alpha, k}$ is the α^{th} quantile of the Chi-square distribution with k degrees of freedom.

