2.1 Data analysis general information

The statistical analysis will be performed by Novartis personnel, using SAS Version 9.4 or above.

Summary statistics for continuous variables will include N, mean, standard deviation, minimum, first quartile, median, third quartile, maximum.

Summary statistics for categorical variables will be presented in contingency tables and will include frequencies and percentages.

The p-values will be presented as one-sided with level of significance 2.5%. 95% confidence intervals will be displayed and will always be two-sided.

The primary analysis may be conducted when all participants have completed their Week 24 visit or discontinued early and when a minimum of 150 participants across both Phase 3 pivotal studies (A2301 and A2302) have completed the 52 week treatment period. Details are given in this document.

The final analysis will be performed based on the final database lock when all participants have completed the study or discontinued early.

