2.7.1.1 Adverse events of special interest / grouping of AEs

Adverse events of special interest (AESI) for remibrutinib (such as risks defined in the Safety Profiling Plan, Risk Management Plan or topics of interest regarding signal detection or routine analysis) will be defined based on the latest Case Retrieval Strategy (eCRS). The comprehensive search of AESI will be performed for all TEAEs.

The number (and percentage) of participants with AESI will be summarized by safety topic of interest (i.e. risk name) and PT for study period and treatment group. Exposure adjusted incidence rate will also be provided by treatment group for the double-blind period and the entire study period.

In addition, for the selected AESIs (Infections, Bleeding, Cytopenias), the number of AESI events will be summarized by safety topic of interest (i.e., risk name) for study period and treatment group.

Summaries will also include the exposure adjusted occurrence rate and the corresponding 95% CI, the number of events per participant, time to onset of first event, duration of the events, the severity of the events, the outcome of events, treatment related events, the action taken with the study treatment for each event and duration of study drug interruption for events leading to study drug interruption.

- Exposure Adjusted Occurrence Rate (EAOR) will be calculated as follows:

EAOR = $100 * \text{total number of events} / \text{total exposure subject-time (years)}$

The exact Poisson 95% CIs (Garwood 1936, Sahai and Khurshid 1993) will be used. Please see [Section 5.4.2.5](#) for details.

For duration of study drug interruption (in days), once the events leading to study drug interruption are selected, the drug interruption occurred within 7 days of the event onset date will be considered. If there are more than one interruption, only the first interruption will be considered.

For the selected AESIs (Infections, Bleeding, Cytopenias), during the double-blind period, the number of events (per risk name), EAOR, and number of participants at risk occurring between 0-≤4 weeks, 4-≤12 weeks, 12-<24 weeks will be displayed by treatment group.

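### The exact Poisson interval for the exposure-adjusted occurrence rate is too narrow if events cluster within participants; this matters mainly for infections and longer follow-up

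*SAP*

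**What the plan says.** SAP 2.7.1.1 singles out three risks for event counts: "for the selected AESIs (Infections, Bleeding, Cytopenias), the number of AESI events will be summarized by safety topic of interest". Among the statistics it lists are "the exposure adjusted occurrence rate and the corresponding 95% CI" and "the number of events per participant", so repeat events are foreseen. On the interval it says: "The exact Poisson 95% CIs (Garwood 1936, Sahai and Khurshid 1993) will be used". SAP 2.1 fixes the level and sidedness: "95% confidence intervals will be displayed and will always be two-sided".

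SAP 5.4.2.5 gives the method. The rate is D/T, where "D is total number of events" and T is total exposure time. The model is one constant intensity: "The number of occurrences of the event will be modeled to follow approximately a Poisson process with constant intensity". The limits are chi-square quantiles with 2D and 2D+2 degrees of freedom, divided by 2T. No participant-level term, robust variance or bootstrap appears in either section.

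SAP 5.4.2.4 uses identical limits for EAIR, but there D is the number of participants with at least one event, so repeats cannot enter. SAP 5.4.2.3 chooses a negative binomial model for the efficacy counts because it "accounts for any over dispersion that may result from assuming a Poisson distribution by allowing a different Poisson rate for each patient".

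**The concern.** A Poisson interval on a total count is valid when the variance of the total equals its mean. That holds for repeat events only if every participant has the same rate and one event does not make another more likely in the same person. When participants differ, the variance exceeds the mean and an interval based on D alone understates the uncertainty. Limits that suit a first-event rate therefore do not transfer automatically to an all-event rate. One further possible source of clustering is that the rule joining consecutive records of the same adverse event (SAP 2.7.1.2) is stated only for the registry tables. No stated rule stops split records of one episode from counting separately in EAOR.

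Infections and bleeding are named potential risks in Protocol 4.5. EAOR is the only planned rate with an interval that counts all events for the selected risks. Readers will set the two arms' intervals side by side, and intervals that are too short would misstate certainty, whether the figures look alarming or reassuring.

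**Working it through.** **Inputs.** Arms of 300 and 150, 24-week double-blind period, 52 weeks in total (SAP 1.1). Infections in Phase 2b: 24.0% on any remibrutinib dose, over up to 12 weeks. Infections in the open-label extension: 23% over a median exposure of 35.14 weeks, at 100 mg b.i.d. Bleeding in Phase 2b: 6.7% on remibrutinib and 2.4% on placebo, read as proportions of participants. All of these are in Protocol 4.5. Assumption: a participant's count has mean μ and variance μ + kμ² (negative binomial). No value of k is given, so k = 0, 0.5, 1 and 2 are shown.

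**Step 1, the plan's own figure.** T = 300 × 24/52.18 = 138.0 subject-years. At k=0, summing the Garwood interval's coverage over the Poisson distribution of D gives 95.3% (infections, remibrutinib), 95.5% (infections, placebo), 96.4% (bleeding, remibrutinib) and 95.9% (bleeding, placebo). The formula delivers its nominal 95% under its own assumption.

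**Step 2, mean count.** With p the proportion having at least one event, μ = [(1−p)^(−k) − 1]/k over the source period, scaled in proportion to time. Phase 2b infections at k=1: 1/0.76 − 1 = 0.316, × 24/12 = 0.632. Extension infections at k=1: 1/0.77 − 1 = 0.299, × 24/35.14 = 0.204.

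**Step 3, inflation and coverage.** The variance of D is 1 + kμ times its mean, so the required width is about √(1 + kμ) times the Garwood width. Phase 2b at k=1: √1.632 = 1.28. Extension at k=1: √1.204 = 1.10. Coverage is summed over the negative binomial total of 300 participants:

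| Infections, n=300 | k=0.5 | k=1 | k=2 |
|---|---|---|---|
| 24 weeks, Phase 2b proportion | 92.1% | 88.2% | 79.6% |
| 24 weeks, extension proportion | 94.3% | 93.8% | 90.7% |
| 52 weeks, μ=1.0 (1.0 event per year) | 89.1% | 83.5% | 74.3% |
| 52 weeks, extension proportion | – | 90.4% | 83.8% |

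The third row uses a round assumed rate of 1.0 per year. The Phase 2b proportion itself implies −ln(0.76) ÷ (12/52.18) = 1.19 per year at k=0, which would lower coverage further, but it stretches 12-week data more than fourfold. On placebo (n=150) the 24-week Phase 2b figures are 92.6%, 90.1% and 82.6%.

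**Step 4, bleeding at 24 weeks.** Remibrutinib: 95.5%, 93.7% and 92.5% at k=0.5, 1 and 2. Placebo: 95.6%, 95.4% and 94.8%. Fewer events mean a smaller μ and less inflation, and the exact interval's conservatism offsets part of the rest. Carried to 52 weeks at k=2, remibrutinib bleeding has μ = 0.0744 × 52/12 = 0.322 and inflation 1.64, with coverage about 88%. Cytopenias were not computed.

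**Step 5, one constructed data set.** Suppose 100 of 300 participants have infections, with 1, 2, 3 and 4 events in 70, 20, 7 and 3 of them. D = 70 + 40 + 21 + 12 = 143 and EAOR = 100 × 143/138.0 = 103.6 per 100 subject-years. Garwood gives 87.3 to 122.1. The sum of squared counts is 261, so the participant-level variance of D is (261 − 143²/300) × 300/299 = 193.5, an inflation of 193.5/143 = 1.35. The robust log-scale interval is 85.6 to 125.4.

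**The case against.** A reader might infer that the planned intervals are simply wrong, for infections and bleeds alike. The documents do not support that. They report no within-participant dispersion for any adverse event, and at k=0 the interval is correct. The overdispersion remark in SAP 5.4.2.3 concerns weekly response counts bounded between 0 and 12, which are different data; it shows that the sponsor knows the issue, not that adverse events are overdispersed. Bleeding holds close to nominal at 24 weeks. This part of the objection stands, so the point is conditional and mainly about infections.

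The infection figures also depend on the source. The extension study has longer follow-up and implies about 0.39 first infections per year (−ln(0.77) ÷ (35.14/52.18)), well below the Phase 2b rate. It used a different dose and population, so neither source is decisive. This stands too, and is why ranges are given.

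A reader might also infer that false safety signals between arms will follow. The SAP plans no EAOR ratio, difference, test or decision rule, and safety lies outside the testing hierarchy. The same risks also get crude incidence and EAIR, which repeats cannot distort, and the events-per-participant summary lets readers see clustering. The harm is limited to how a descriptive interval is read.

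None of this answers the central point: the stated rule has no protection if events do cluster.

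**Conclusion.** The point holds as a conditional one. SAP 5.4.2.5 treats all events as independent with a common rate, and its interval is too narrow if participants differ in risk or events recur in the same people. For infections in an arm of 300 at 24 weeks, the nominal 95% becomes about 92–94%, 88–94% or 80–91% for k of 0.5, 1 or 2. At 52 weeks it becomes about 84–90% (k=1) or 74–84% (k=2), because the inflation 1 + kμ grows with follow-up. Bleeding at 24 weeks stays at about 92–96% up to k=2.

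These figures rest on assumed values of k, a gamma spread of participant rates, complete follow-up, event rates proportional to time, and the extension's median exposure treated as common to all. They illustrate size and do not predict it. The point estimate D/T, EAIR, crude incidence and all efficacy conclusions are untouched.

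**What to change.** In SAP 5.4.2.5, compute the EAOR interval with a participant-level variance: a log-link rate model with log(time) as offset and robust variance by participant, or a bootstrap that resamples participants. Keep Garwood for EAIR.

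Use one method for both arms within each risk table. Keep Garwood for a risk, in both arms together, when either arm has too few events for the robust method, and fix that threshold before the analysis. A switch made arm by arm would be a mistake: extrapolating Phase 2b bleeding to 24 weeks at k=0 gives about 42 events on remibrutinib and 7 on placebo, which could put two methods in one table.

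The cost is a short SAP edit, a few lines of code and somewhat wider intervals where events cluster. Where they do not, the result should stay close to Garwood.

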5.4.2.6 Confidence interval for proportion of binary data

Confidence intervals for proportion of binary data including observed response rate and adverse event incidence rate will be derived as well based on the score method including continuity correction ([Newcombe, 1998](#)):

With Z as $(1-\alpha/2)$ -quantile of the standard normal distribution (SAS: $z = \text{PROBIT}(1-\alpha/2)$), n as total number of subjects (i.e. number of subjects in the denominator), and p as estimated crude incidence (number of subjects with event / n) it is $q = 1 - p$

Then the lower limit is for $p > 0$, ($L = 0$ for $p = 0$),

$$L = \max \left(0, \frac{2np + z^2 - 1 - z\sqrt{z^2 - 2 - \frac{1}{n} + 4p(nq + 1)}}{2(n + z^2)} \right)$$

and the upper limit is for $p < 1$, ($U = 1$ for $p = 1$),

$$U = \min \left(1, \frac{2np + z^2 + 1 + z\sqrt{z^2 + 2 - \frac{1}{n} + 4p(nq - 1)}}{2(n + z^2)} \right).$$

5.4.3 Multiple imputations

Multiple imputation is a simulation-based approach where missing values are replaced by multiple Bayesian draws from the conditional distribution of missing data given the observed data and covariates, creating multiple completed data sets. These completed data sets can then be analyzed using standard methods. [Rubin \(1987\)](#) presented rules how to combine the multiple sets of estimates to produce overall estimates and confidence intervals that adequately incorporate missing data uncertainty. The multiple imputation analysis will be imputed based on the individual treatment arm information.

Missing values for UAS7/HSS7/ISS7/AAS7/DLQI will be imputed separately. The imputation is done on the original post-baseline score and the imputation model will include treatment group, the corresponding baseline score, actual randomization strata variables, week and both interaction of treatment by week and interaction of the corresponding baseline score by week. The number of imputations is 100. The imputed values may exceed possible range of variables. In this case, the imputed values which exceed possible maximum value (e.g., 42 for UAS7) will be replaced with the maximum value, the imputed values which exceed possible minimum value (e.g., 0 for UAS7) will be replaced with the minimum value.

Multiple imputation will be implemented using the RMConjPlus20 and RefBTBV04 SAS macro. The macros are available from the website of London school of Hygiene & tropical

medicine (LSHTM) on <https://www.lshtm.ac.uk/research/centres-projects-groups/missing-data#dia-missing-data>. The purpose and activities of each of the two macros is described below. For more details of these two macros please see “The RMConjPlus and RefbTbV SAS macros” by James H. Roger (2023) at <https://www.lshtm.ac.uk/research/centres-projects-groups/missing-data#dia-missing-data>.

The %RefBTBV SAS macro is used to set up the design matrix for reference-based imputation. This macro creates an input data set for %RMConjPlus by generating the required Treatment*Visit part of the design matrix based on the chosen reference-based imputation method (J2R, CIR, CR, etc.).

The %RMConjPlus SAS macro is applied for reference-based imputation (J2R in this study) where an individual patient’s means model for those on active treatment is modified after trial withdrawal to closer represent the reference (placebo) arm (Carpenter, 2013). The imputation is done by two stages. In stage 1, it fits a Bayesian Repeated Measures model where there are a fixed number of visits. A multivariate Normal model is assumed with a series of one or more unstructured covariance matrices. Each subject uses only one of these matrices. Data within subject are related while data between subjects are assumed independent. In stage 2, it builds a set of imputed values for missed observations directly as part of the MCMC process using an pre-specified imputation model (J2R in this study).

This is example code to implement the primary analysis:

```
%RefbTBV(  
Data= inputdata,  
Out=RefB_Out,  
Subject= usubjid,  
Visit= week,  
OnTreatment= OT,  
Treatment= group,  
Method= Mymethod,  
Reference= Placebo);
```

where usubjid = unique subject identifier

week =study week
group= planned treatment group
(1 = LOU064 2 = Placebo)
OT = indicator of on/off treatment status

Mymethod = Method used to impute missing data. For example, this could be specified as J2R to indicate that Jump to reference is used to impute missing data for LOU064 patients who discontinued treatment and MAR otherwise, where Placebo is used as reference.

```
%RMConjPlus (  
Data=RefB_Out ,  
OUT_Imp= out_imp,  
Subject=usubjid,  
Visit=week,  
Response=aval,  
Model=&RefbTbV base*week antige region,  
Class=week group antige region,
```

```
seed=23012,  
Nimpute=100  
) ;
```

Where usubjid = unique subject identifier
week = study week
aval = UAS7 weekly score
base = baseline UAS7 score
antige = prior exposure to anti-IgE biologics
region = geographic region
&RefbTbV = design matrix generated from RefbTBV macro.

If the imputation model has warnings regarding auto-correlation, a larger number of autocorlag parameter could be specified (e.g., autocorlag=70 in the RMConjPlus macro). Any missing baseline values will be multiply imputed using baseline characteristics variables before putting into the %RefBTBV and %RMConjPlus using Proc MI. The example code for imputing baseline of DLQI is shown below:

```
proc mi data= dlqi_base_imp out=dlqi_regpmm nimpute = 100 seed = 23012;  
class group sex antige region;  
FCS regpmm(base/details);  
var age sex group antige region base ;  
run;
```

Where group= planned treatment group
(1 = LOU064 2 = Placebo)
age = age at screening of study participants
sex = gender of study participants
antige = prior exposure to anti-IgE biologics
region = geographic region
base = baseline DLQI score

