2.5.1.1 Primary endpoint

The primary clinical question of interest is: What is the effect of remibrutinib treatment versus placebo on the change from baseline in UAS7 score at Week 12 after treatment in adult participants with CSU who are inadequately controlled by H1-antihistamine and receiving a stable locally label approved dose of a second generation H1-antihistamine, regardless of treatment discontinuation for any reason and regardless of intake of a different second generation H1-antihistamine as rescue medication and considering strongly confounding prohibited medication as an unfavourable outcome?

The primary efficacy endpoint is the absolute change from baseline in **UAS7 score at Week 12**, which is the UAS7 score at Week 12 minus the UAS7 score at baseline. The UAS7 is the sum of the HSS7 score and the ISS7 score, and ranges from 0-42. Weekly scores (HSS7 and ISS7 scores) will be derived by adding up the average daily scores of the 7 days preceding the visit.

Derivation of UAS7

HSS and ISS are recorded by the participant twice daily (morning, evening) in their eDiary, on scale of 0 to 3.

The daily score of HSS and ISS will be calculated by averaging the morning and evening HSS and ISS score, respectively (possible range 0-3). If one of the morning or evening scores is missing, the non-missing score for that day (morning or evening) will then be used as the daily score. If both of the morning and evening scores are missing, the daily score for that day will be missing.

If the questionnaires in eDiary are completed more than once per session (morning, evening) on the same day, then the worst score will be used for that day.

HSS7 and ISS7

The weekly score of HSS and ISS (HSS7 and ISS7) will be derived by adding up the daily HSS and ISS scores of the 7 days preceding the visit, respectively (please refer to the assessment window in [Section 2.1.1.5](#)). If one or more of the daily scores are missing, the following principles will be applied to handle the missing data:

- If a participant has at least 4 non-missing daily scores within the 7 days, HSS7 or ISS7 will be calculated as the sum of the available scores of that week, divided by the number of non-missing days, multiplied by 7.
- If there are less than 4 non-missing daily scores within the 7 days, HSS7 or ISS7 will be considered as missing for that week.

UAS7

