2.5.1.4 Handling of missing values

Missing data imputation will be performed for the analyses when using statistical model.

Handling of missing RDO data

If no RDO data was collected after study treatment permanent discontinuation, missing data will be imputed based on the following rules:

- For participants in the active treatment arms, if sufficient RDO data, missing data will be imputed using MI based on observed RDO data in the corresponding active arm. If not feasible (e.g., very limited RDO data), missing data will be imputed based on observed data in the placebo arm under the assumption of jump to reference (J2R) using MI.
- For participants in the placebo arm, if sufficient RDO data, missing data will be imputed using MI based on observed RDO placebo arm data. If not feasible (e.g., very limited RDO data), missing data will be imputed using MI under the MAR assumption based on the observed placebo arm data.

Handling of other missing data

If there is any missing data prior to Week 12, the missing data will be handled following the MAR assumption.

The detailed steps for handling of the intercurrent events and analyses are described below.

Step 1: Identify the participants with intercurrent events.

Step 2: For participants with intercurrent event 1 (Discontinuation of study treatment prior to Week 12 due to any reasons), determine the imputation strategy based on the amount of RDO data.

- Calculate the percentage of RDO data available at Week 12 in participants with intercurrent event 1 by treatment group
- If $\geq 50\%$ of participants had RDO data at Week 12, consider RDO data is sufficient
- If $< 50\%$ of participants had RDO data at Week 12, consider RDO data is not sufficient

Step 3: Perform the missing data imputation.

- For participants with intercurrent event 3 (Intake of strongly confounding prohibited medication), set missing at all visits after the event
- Perform the missing data imputation under MI framework according to the imputation strategy on Step 2. At the same time, missing data imputation of other missing data (i.e., non RDO data) will also be performed. The details on MI are described in [Section 5.4.3](#)

- Replace the values at all visits after the intercurrent event 3 with the worst value

Step 4: Perform the analysis.

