UAS7 \leq 6 at Week 12	Odds ratio between treatment groups	A treatment policy strategy: RDO data or data collected after the IE will be used. In case of missing values of RDO data, derivation based on the multiply imputed UAS7 described in Section 2.5.1.3 will be applied.
		A composite strategy: UAS7 response after the intercurrent event will be excluded and UAS7 \leq 6 will be derived from imputed UAS7 score using the worst value (i.e., 42).
UAS7 = 0 at Week 12	Odds ratio between treatment groups	Same as UAS7 \leq 6 at Week 12.
ISS7 score change from baseline to Week 12	Mean difference between treatment groups	Same as the primary estimand, see Section 2.5.1.3
HSS7 score change from baseline to Week 12	Mean difference between treatment groups	Same as the primary estimand, see Section 2.5.1.3
UAS7 \leq 6 at Week 2	Odds ratio between treatment groups	Same as UAS7 \leq 6 at Week 12.

Endpoint	Summary measurement	Handing of intercurrent event
		Note: As this endpoint is for the score at W2, some intercurrent events, e.g. intake of strongly confounding prohibited medication, will not be considered.
DLQI 0/1 at Week 12	Odds ratio between treatment groups	Same as UAS7 \leq 6 at Week 12. In case of missing values of RDO data, derivation based on the multiply imputed DLQI score with same approach as UAS7 will be applied.
Cumulative number of weeks with an UAS7 \leq 6 response between baseline and Week 12	Ratio of response rate between treatment groups	Same as UAS7 \leq 6 at Week 12. Derivation based on the multiply imputed UAS7 described in Section 2.5.1.3 will be applied.
Cumulative number of weeks with an AAS7=0 response between baseline and Week 12	Ratio of response rate between treatment groups	Same as UAS7 \leq 6 at Week 12. Derivation based on the multiply imputed AAS7 with same approach as UAS7 will be applied.

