2.5.2.4 Handling of missing values

See [Section 2.5.1.4](#) for missing data of continuous variables. Missing data of response variables will be derived using the multiply imputed data for corresponding continuous variables.

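### Does clipping normal-model imputations at 0 distort the UAS7=0 endpoint enough to need another analysis?

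*SAP*

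**What the plan says.** SAP 5.4.3 imputes the original post-baseline score separately for each instrument, with 100 imputations. On the model it says: "A multivariate Normal model is assumed with a series of one or more unstructured covariance matrices". Draws outside the scale are moved to its ends. At the lower end, "the imputed values which exceed possible minimum value (e.g., 0 for UAS7) will be replaced with the minimum value", so a negative UAS7 draw becomes 0.

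The responder endpoints inherit these draws. SAP 2.5.2.4 states: "Missing data of response variables will be derived using the multiply imputed data for corresponding continuous variables". Table 2-12 in SAP 2.5.2.1 repeats this for UAS7 responses: "In case of missing values of RDO data, derivation based on the multiply imputed UAS7 described in Section 2.5.1.3 will be applied". No rounding is described, so an imputed 0.3 is a non-response for UAS7=0.

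The route by which a missing value is imputed depends on the case:

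- Gaps unrelated to missing retrieved drop-out (RDO) data: "If there is any missing data prior to Week 12, the missing data will be handled following the MAR assumption" (SAP 2.5.1.4).
- Remibrutinib discontinuers without RDO data: imputed from RDO data in that arm if these are sufficient, otherwise by jump to reference (J2R). The example in SAP 5.4.3 reads "Jump to reference is used to impute missing data for LOU064 patients who discontinued treatment and MAR otherwise".
- Placebo discontinuers without RDO data: imputed from placebo RDO data if sufficient, otherwise "missing data will be imputed using MI under the MAR assumption based on the observed placebo arm data".

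A week is missing only when the diary is very incomplete: "If there are less than 4 non-missing daily scores within the 7 days, HSS7 or ISS7 will be considered as missing for that week" (SAP 2.5.1.1). One of the two entries on a day is enough for a daily score.

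SAP 2.5.2.5 and 2.6.2.5 plan no sensitivity analysis for the secondary endpoints in either scenario.

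**The concern.** UAS7=0 at Week 12 is a confirmatory endpoint in both testing strategies (H03 with UAS7 as primary, H04 with ISS7 and HSS7 as co-primaries). SAP 3.2 expects a large point mass at zero: 0.35 on remibrutinib and 0.10 on placebo. A continuous normal distribution has no point mass. After clipping, its zero share is simply the area below 0, which is governed by the mean and SD and not by how many patients are symptom-free. The responder rate among imputed patients could therefore be well off in both arms, and by different amounts.

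Nothing planned isolates this. The supplementary analysis in SAP 2.5.2.6 only changes the effect scale. The sensitivity analysis for the primary endpoint only changes the value given after strongly confounding medication. The observed rates covered by SAP 5.4.2.6 can be set beside the imputed ones, but that gap also contains J2R and worst-value patients.

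**Working it through.** **Inputs.** From SAP 3.1 and 3.2: UAS7=0 rates 0.35 and 0.10; UAS7≤6 rates 0.53 and 0.15; mean difference 10; 300 and 150 randomised; 10% drop-out, leaving 270 and 135. The MAR share, the Week 12 means and the score shape are not in the documents and are assumed below.

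**1. The plan's own figure.** For 0.35 against 0.10 with 270 and 135, one-sided 0.025 and continuity correction, power is above 99.99%. This agrees with the stated figure of more than 99%.

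**2. Zero share produced by clipping, remibrutinib.** Take a normal variable censored at 0 that meets both planned rates, Φ(-μ/σ) = 0.35 and Φ((6-μ)/σ) = 0.53. The solution is μ = 5.02, σ = 13.03. The censored score then has mean 8.09 and SD 9.25. A normal model with that mean and SD puts Φ(-8.09/9.25) = 0.19 at or below 0, against 0.35.

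Simulated imputation of Week 12 given 0 to 11 earlier weeks gives 0.185-0.214. A wider set of shapes gives 0.17-0.23. Using SD 12 with assumed Week 12 means of 7 to 13 gives 0.14-0.28. All are below 0.35.

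**3. Loss per MAR-imputed patient.** In 18 simulated scenarios that all meet the planned rates and the difference of 10, the zero share is 0.18-0.21 on remibrutinib and 0.04-0.06 on placebo. The loss is 0.14-0.17 and 0.03-0.06 per imputed patient. These scenarios assume data missing completely at random and use an unadjusted odds ratio.

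**4. Effect on the remibrutinib rate.** Loss in the rate = MAR share × loss per patient.

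| Assumed MAR share | Fall in the remibrutinib rate (simulated) |
|---|---|
| 2% | 0.28-0.34 point |
| 3% | 0.43-0.49 point |

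**5. Effect on the treatment comparison.** The planned odds ratio is (0.35/0.65)/(0.10/0.90) = 4.85. The yardsticks at 300 and 150 are:

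- SE of the difference = √(0.35×0.65/300 + 0.10×0.90/150) = 3.69 points.
- SE of the log odds ratio = √(1/105 + 1/195 + 1/15 + 1/135) = 0.298.

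*Equal shares, 3% in both arms (simulated).* The difference falls by 0.27-0.35 point, which is 0.07-0.09 SE. The odds ratio changes by -0.1% to -0.7%, at most 0.02 SE on the log scale.

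*Unequal shares, 3% on remibrutinib and 10% on placebo.* SAP 2.5.1.4 leads towards this case if RDO data are insufficient, because placebo drop-outs then go to MAR and remibrutinib drop-outs do not. The remibrutinib rate falls by 0.43-0.49 point and placebo by 0.3-0.5 point.

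| Remibrutinib | Placebo | Difference moves | Odds ratio changes | SE of log odds ratio |
|---|---|---|---|---|
| 0.3451 | 0.097 | -0.19 point | +1.2% | 0.04 |
| 0.3457 | 0.097 | -0.13 point | +1.5% | 0.05 |
| 0.3451 | 0.095 | +0.01 point | +3.6% | 0.12 |
| 0.3457 | 0.095 | +0.07 point | +3.9% | 0.13 |

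The sign for the odds ratio reverses between the two cases, so a uniformly conservative bias is not established. J2R draws are clipped too. They are left out here, and including them would lower the remibrutinib rate further and pull the second case back towards balance.

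**6. Power after the loss.** With rates of 0.3451 and 0.10, or with any of the last table's pairs, power at 270 and 135 is still above 99.9%.

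**The case for a change.** The strongest case for acting is that the defect can be demonstrated and is cheap to examine. Roughly two in five of the zeros expected among MAR-imputed remibrutinib scores are lost (0.14-0.17 of 0.35). The endpoint is confirmatory and no planned analysis addresses the imputation model. Within-arm predictive mean matching brought the imputed zero shares back to 0.33-0.35 and 0.10-0.11 in simulation, and the SAP already uses that technique for missing baseline DLQI.

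The mechanism and the missing check stand. The argument weakens on what the extra analysis would deliver:

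- It would leave the confirmatory imputation as it is and quantify a shift of about a tenth of a standard error.
- The choice of method is a preference. Non-responder imputation or direct imputation of the binary response would serve as well. Matching on placebo would draw on about 14 zero scores (0.10 × 135), so donors would repeat.
- Deriving all responses from one set of imputed scores keeps UAS7, UAS7≤6 and UAS7=0 mutually consistent. The amendment history shows that the method for missing responses was revised in Amendment 2, so this was a considered choice.
- Formal testing takes place only at the primary analysis (SAP 2.13), and the latest SAP amendment is dated before the final analysis. An addition now could only be supportive and would have to be labelled as not pre-specified.

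Nor can the effect be enlarged by placing the whole planned 10% drop-out under MAR in both arms. The SAP does not send remibrutinib discontinuers down that route.

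**Conclusion.** No change is needed. Clipping does under-produce exact zeros among MAR-imputed scores: about 0.18-0.21 against 0.35 on remibrutinib and 0.04-0.06 against 0.10 on placebo, under the assumed shapes. Few scores should be affected, because four diary days make a valid week and remibrutinib discontinuers are imputed by other routes.

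At an assumed 3% MAR on remibrutinib, that arm's rate falls by 0.43-0.49 point. The odds ratio changes by -0.1% to -0.7% with 3% on placebo, and by +1.2% to +3.9% with 10% on placebo. The larger figure is 0.13 SE of the log odds ratio. Neither power nor the order of testing is affected.

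This rests on the planning rates in SAP 3.2, on assumed MAR shares, and on MAR-imputed participants resembling the rest of their arm. A single coherent imputation that reproduces the mass at zero imperfectly is a fair trade-off at this size.
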